7.1 Study Design

Describe and explain the study design.

Aim 1: Pilot test the effect of SABL in reducing agitation in persons with dementia. This is a crossover, cluster randomized control trial to pilot test the effect of SABL in NHs. This design includes a 4-week intervention period and 2-week washout period. This design will allow for participants to act as their own control and thus reduce the needed sample size and strengthen the research rigor. The study procedures include five phases over 13 weeks. We will recruit a total sample of 40 nursing home residents with dementia and agitation from the 2 nursing homes, 20 residents from each nursing home. The two NHs will be randomly assigned into different sequences for intervention and control. Otherwise, the same study procedures will be

conducted simultaneously at the two NHs. During the daytime, participants will be guided and encouraged to spend time in the designated areas in the dining room and activity room for their meals and daily activities. For blinding prior to control period, we will perform installation procedures with non-SABL light bulbs. We will evaluate the effect of SABL on agitation, other BPSD, affect, and sleep, based on the actual lighting levels participants receive measured by personal light monitors. The study procedures include five phases: 1) baseline, 2) intervention, 3) post intervention/washout, 4) control, and 5) post control/washout. The sequence of intervention and control differs between the two NHs based on randomized assignment. Agitation and lighting will be measured at baseline and then once every two weeks throughout the study. We hypothesize that participants will show less agitation during and after SABL compared to baseline and control periods. We will also explore the intervention effect on other BPSD and affect and monitor adverse effects. **Aim 2: Evaluate the fidelity of the SABL delivery.** We will evaluate the fidelity of SABL delivery by measuring lighting intensity (lux) and CS levels in two ways: 1) on-site light measurements, and 2) a personal light monitor. The actual lighting data will be compared to the intended SABL design.

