- 1) Data extraction from CMS Nursing Home Compare Website (<https://www.medicare.gov/care-compare/>): Data on facility characteristics, including number of certified beds, ownership, quality rating, participation in Medicaid, staffing, COVID-related data is publicly available and can be accessed through the link provided above.
- 2) Chart reviews: Data on resident characteristics, including age, race, sex, diagnoses, level of cognitive impairment, current medication use, current listed comorbidity and physical function, BPSD in the past two weeks, pain in the past two weeks, current vision status, current hearing status, and other clinical conditions.
- 3) Surveys based on staff caregivers' reports: The surveys will be conducted on paper and in-person with researcher administering the survey to the staff caregiver for proxy report of residents' dementia stage, agitation, other BPSD, affect, and side effects.
- 4) Personal light monitor, LYS button, placed on individual resident participants to measure lighting intensity (lux) and CS levels participants receive.

There will be seven visits for data collection throughout the 13-week of the study: baseline visit (week 1) and six follow-up visits, every other week (weeks 3, 5, 7, 9, 11, 13). The procedures for each visit are as follows:

Baseline visit: Procedures 1 through 4.

Follow-up visits: Procedures 3 and 4.

For the procedure 4, the light monitor will be worn 7 days a week during the data collection weeks (week 1, 3, 5, 7, 9, 11, & 13).

Aim 2: We will evaluate the fidelity of SABL delivery by measuring lighting intensity (lux) and CS levels.

Data collection procedures will include the following:

- 1) on-site manual light measurements
- 2) personal light monitor, LYS button, placed on individual resident participants (same as the procedure 4 in aim 1).

The procedures will be conducted primarily on site at the nursing home facilities.

The procedure 1 will be conducted twice a week throughout the 13-week study period.

For the procedure 2, as mentioned in aim 1, the light monitor will be worn 7 days a week during the data collection weeks (week 1, 3, 5, 7, 9, 11, & 13).

Aim 3: Staff and Administrators

Data collection methods include the following:

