7.4.3 Method for Assigning Subject to Treatment Groups

Describe the randomization process and how the associated treatment assignment will be made.

The study design is a crossover, cluster randomized controlled trial. We plan to conduct the study in two nursing homes. The study procedures include five phases over 13 weeks (Table). The two NHs will be randomly assigned into different sequences for intervention and control. Otherwise, the same study procedures will be conducted simultaneously at the two nursing homes. During the daytime, participants will be guided and encouraged to spend time in the designated areas in the dining room and activity room for their meals and daily activities.

Table. Intervention testing procedures and timeline.

Week	1	2	3	4	5	6	7	8	9	10	11	12	13
------	---	---	---	---	---	---	---	---	---	----	----	----	----

Study phases	NH A	Baseline	Intervention		Post intervention/washout		Control			Post control	
	NH B		Control		Post control/washout		Intervention			Post intervention	
Lighting	Usual light		I: SABL C: Usual light		Usual light		C: Usual light I: SABL			Usual light	
Data collection	Baseline, L&E		L&E	L&E		L&E		L&E	L&E		L&E

L=lighting measured via individual light monitor, E=effect outcomes (e.g., agitation, BPSD, affect, and sleep) and adverse effects

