8.3 Statistical or Analytic Methods

Describe the statistical methods (or non-statistical methods of analysis) that will be employed.

Aim 1

All data will initially be assessed with descriptive techniques to determine distributions and identify outliers. Baseline to post-intervention changes in participants' CMAI, NPI-NH, and ARS scores will be used as the outcomes in all subsequent analyses. To conduct the group analysis, each participant will serve as their own control, which allows minimal use of control variables. The effect of the intervention will be analyzed using multi-level modeling to adjust for clustering of participants at the facility level. We will use the daytime and nighttime average of lighting dosages (lux and CS) from the personal light monitors as the independent variable to analyze the effect of SABL on changes in CMAI, NPI, and ARS. Although not powered for a detailed analysis, we will explore the impact of participant characteristics (sex, age, race, ethnicity, ADRD stage, and daylight exposure) on the intervention effect by adding them as covariates to the regression model.

Aim 2

All data will initially be assessed using descriptive techniques to examine underlying assumptions and detect any violations. To assess the intervention fidelity, the lux and CS data measured via manual measurements will be analyzed using one sample t-tests to analyze lighting levels during the day and nighttime, compared to the target levels. The data from personal light monitors will be analyzed similarly at individual level. Although not powered for a detailed analysis, we will explore the impact of participant characteristics (e.g., sex, age, race, dementia stage, comorbidity, facility, and daylight conditions) on the lighting received based on the personal light monitor.

Aim 3

Quantitative Analysis: The data include ratings of acceptability, feasibility, appropriateness, time, and cost of installing and maintaining the intervention. All data will be analyzed using descriptive analyses. Although not powered for a detailed analysis, we will explore differences in perceptions of intervention feasibility and acceptability between sexes as well as the difference across professional roles and between facilities.

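### Aim 1's model names only the facility level: with several change scores per resident its standard errors are wrong, and with one baseline-to-post change the control period goes unused

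*Protocol*

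**What the plan says.** Protocol 8.3 (Aim 1) and the SAP (Aim 1) carry the same text.

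- **Model:** "The effect of the intervention will be analyzed using multi-level modeling to adjust for clustering of participants at the facility level". No other level is named.
- **Outcome:** "Baseline to post-intervention changes in participants", for the CMAI, NPI-NH and ARS. The number of changes per resident is not given.
- **Own control:** "each participant will serve as their own control, which allows minimal use of control variables". No model term is attached to this.
- **Regressor:** "We will use the daytime and nighttime average of lighting dosages (lux and CS) from the personal light monitors as the independent variable".

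On the design, Protocol 7.4.3 says "The two NHs will be randomly assigned into different sequences for intervention and control", so there is one home per sequence. Protocol 7.2 says "There will be seven visits for data collection throughout the 13-week of the study": a baseline and weeks 3, 5, 7, 9, 11 and 13. Protocol 7.1 justifies the crossover thus: "This design will allow for participants to act as their own control and thus reduce the needed sample size and strengthen the research rigor". Its hypothesis is "We hypothesize that participants will show less agitation during and after SABL compared to baseline and control periods", while Table 1 labels the visits at weeks 7 and 13 as post intervention or post control, with week 7 also counted as washout. Neither document says how those two visits enter the analysis.

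**The concern.** The crossover earns its efficiency from comparing each resident under SABL with the same resident under control. A model delivers that only if it holds a resident effect, or works on within-resident differences, and says which periods are compared. The stated model does neither. Three readings are open:

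- **(a) One change per resident, baseline to post-intervention.** This is what the text names. It raises no repeated-measures problem, but the control period drops out.
- **(b) Two or more changes per resident.** All subtract the same baseline score, so they are correlated. A facility-only model treats them as independent within a home.
- **(c) One SABL-minus-control difference per resident.** This fits the own-control wording and avoids the correlation, but the text does not name it.

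At stake are the power of the on/off comparison and the false-positive rate of the dose analysis. The open choice could also be settled after the data are seen.

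**Working it through.** **Inputs.** From the documents: 40 residents, 20 per home, 10% attrition, final n = 36, alpha 0.05, d = 0.53, power 0.92 (Protocol 8.2); two homes; six follow-ups. Assumed, because the documents give no value: 18 residents per home, exchangeable errors, and how much dose varies between residents.

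**1. The plan's own power.** A paired t test with d = 0.53 gives:

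- n = 36, two-sided: 0.871
- n = 36, one-sided: 0.930
- n = 40, two-sided: 0.905 (0.918 by normal approximation)
- two independent groups of 18, two-sided: 0.36

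The stated 0.92 therefore fits only a within-resident comparison (one-sided at 36, or at the 40 enrolled).

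**2. Correlation between changes.** Let scores have variance s² and correlation r. A change is C_j = Y_j − Y_0, so Var(C_j) = 2s²(1 − r) and Cov(C_j, C_k) = s²(r − r − r + 1) = s²(1 − r). The correlation is 0.5 whatever r is.

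**3. On/off contrast, two changes (one SABL, one control).** The true variance of the contrast carries a factor (1 − 0.5) that the facility-only model omits. Its standard error is too large by 1/√(1 − 0.5) = 1.41.

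- Type I error: 2[1 − Φ(1.96 × 1.41)] = 0.6%; by simulation 0.7% with two, four or six changes.
- Power at d = 0.53: Φ(0.53 × 6 − 1.96 × 1.41) = Φ(0.41) = 0.66; by simulation 0.64, against 0.87 with a resident effect.
- For correlation 0.3 to 0.7, type I error runs from about 2% to 0.1% or less, and facility-only power from 0.79 to 0.34.
- With four or six changes at 0.53 SD, little power is lost (0.95 versus 0.99 with four).

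**4. Personal light dose.** Write dose as the on/off indicator plus a resident constant. The within-resident part has its standard error overstated, as in step 3. The between-resident part has it understated by √(1 + (k − 1) × 0.5) for k changes: 1.22, 1.58 and 1.87 for k = 2, 4 and 6. If dose varied only between residents, type I error would reach 2[1 − Φ(1.96/1.22)] = 11%, and likewise 22% and 29%. Simulated type I error of the facility-only model (nominal 5%), by between-resident dose SD as a fraction of the on/off contrast:

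| Changes | SD 0.25 | SD 0.5 | SD 1.5 |
|---|---|---|---|
| 2 | 2% | 5% | 9–10% |
| 4 | 3–4% | 11% | 20% |
| 6 | 7% | 18% | 28% |

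A random rather than fixed facility term gives almost the same figures at the two SDs where both were run (0.25 and 0.5). A different dose model, with a dose intraclass correlation of 0.5 or 0.9, gives 8% and 11% with two changes and 19% and 28% with six. With an intraclass correlation of zero the error stays near 5%. With resident and visit terms and dose split into resident mean and visit deviation, type I error is about 5% throughout.

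**5. Reading (c).** Power at d = 0.53 is 0.87 with facility fixed. With a facility random intercept it is 0.79 (z test) or 0.59 (Satterthwaite df), because a facility variance that is truly zero is estimated above zero in 32% of samples.

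**6. What the resident model does not cure.** Let facility-by-period variation have SD f, in units of the change-score SD. It adds f² to the variance of the on/off contrast. With two changes the resident-model variance is 0.5/18 = 0.0278. At f = 0.1 the true variance is 0.0378 and type I error is 2[1 − Φ(1.96 × √(0.0278/0.0378))] = 9%. The facility-only model reports 2/36 = 0.0556, which gives 2%.

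| Changes | f | Facility-only | Resident and visit terms |
|---|---|---|---|
| 2 | 0.1 | 2% | 9% |
| 2 | 0.2 | 8% | 21% |
| 4 or 6 | 0.1 | 3–4% | 14% |
| 4 or 6 | 0.2 | 12–16% | 31% |

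**The case against.** The best defence is that this is an incompletely specified pilot rather than a wrong model. The own-control sentence shows that a within-resident comparison is intended. Protocol 7.4.25 promises diagnostics to choose a suitable modelling approach. The reading nearest the text, (a), has no repeated-measures error. All of that is true, and it means the harm is conditional. It does not supply the missing term: the diagnostics sentence names no model and leaves the choice until data are in hand, and reading (a) gives up the comparison with control that 7.1 hypothesises.

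A second objection is that the power figures concern a SABL indicator, while the plan's regressor is dose. That is fair. For dose with two changes and modest between-resident variation, type I error is 2–5%, which is not inflated. The dose problem depends on a quantity the plan does not give.

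The third objection is the most substantial: the facility-only model's oversized standard error partly shields it from facility-by-period variation, and the resident model removes that shield. This stands, and it belongs in the plan as a stated limitation. The shield is accidental, though, and does not work for dose, where the error can run the other way.

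**Conclusion.** The point holds as a conditional one and should be corrected before analysis. Protocol 8.3 and the SAP name facility as the only level and give no resident, visit or condition term. Under reading (a) the control period is unused. Under reading (b) the standard errors are wrong: too large for an on/off contrast (type I error about 0.7%; two-change power about 0.64 rather than 0.87), and in either direction for dose (about 2–10%, 3–20% and 7–28% with two, four and six changes). These figures rest on 36 residents, correlation 0.5 and assumed dose SDs of 0.25 to 1.5 of the on/off contrast.

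Three stronger readings are not supported:

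- A reader might infer that the plan rules out a resident effect. It omits one; it does not exclude it.
- A reader might infer that two homes leave the SABL test with 1 df. That is the df between homes. SABL varies within each home, so it is not the df of the SABL contrast.
- A reader might infer that lost power goes with few changes and false positives with many. Dose error also exceeds 5% with two changes once dose varies enough between residents (about 8% at SD 1.0), and it stays below 5% with four changes at SD 0.25. Between-resident dose variation matters as well as the number of changes.

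**What to change.** In Protocol 8.3 and the SAP:

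1. State which changes or differences enter, and how weeks 7 and 13 are classed in each home.
2. If more than one change per resident enters, fit a random intercept for resident, fixed visit terms and facility as a fixed two-level effect, with small-sample df. If one SABL-minus-control difference per resident is meant, say so and test the equally weighted mean of the two home means. This also cancels a period effect common to both homes.
3. Use SABL condition as the regressor for the crossover contrast. Keep personal light dose for the dose analysis, split into each resident's mean and the visit deviation from it.
4. State that facility-by-period variation cannot be separated from SABL with two homes, that the resident model is more exposed to it (step 6 of the working), and that inference is limited to these two homes.

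The cost is wording; the data and software are unchanged. Visit terms do not raise the on/off standard error in balanced two- and four-change layouts. With six changes they raise it by about 15% (√(48/36) = 1.15). In return they remove a trend bias in that layout of about 0.06 SD if weeks 7 and 13 count as off (on minus off is −6 weeks in one home and +3 in the other, mean −1.5; at an assumed drift of 0.5 SD over 12 weeks, 1.5 × 0.5/12 = 0.0625).

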2.3 Study Rationale

Provide the scientific rationale for the research.

Our SABL is the first ambient lighting intervention that utilizes a smart lighting system to accommodate daylight through windows and maintain the lighting condition, without eliminating the daylighting benefits. This approach is more sustainable and potentially maximizes the effect of the ambient lighting interventions.

This SABL is 'smart' in two aspects. First, designing for ambient lighting environments, compared with simple light boxes, makes adherence easier. Second, the new tunable LED technologies address implementation barriers by providing new auto-controlling of light intensity, distribution,

and spectra in nursing home buildings. The SABL system has a pre-programmed 24-hour control schedule on illuminance settings to mimic the natural bright-dark cycle. It will regularly monitor the lighting level using customized photosensors and automatically adjust the lights to accommodate the daylight effect, minimizing staff burden and maintenance efforts, while maximizing the LI effect. Moreover, we will work closely with the nursing homes and co-design the SABL and implementation protocol and obtain input from stakeholders (e.g., care providers, directors of maintenance, and administrators). This will be a critical foundation to implement the SABL on a larger scale.

Our proposed SABL will provide bright light with illuminance targeted at 400 lux and high CS of 0.3 at the eye level, and dim light \leq 40 lux and low CS \leq 0.1 at night to maintain a bright-dark cycle to regulate activity/rest rhythm, improve sleep, and reduce agitation. This dosage selection is based on the current scientific consensus and research evidence. We will measure the light levels received by each participant using a personal, wearable lighting measure device and will use the actual dosage (lux and CS levels) received by participants to analyze the intervention effect. We design the lighting based on lux and CS levels at the eye level in the sitting position, which is more in line with the surrounding surface reflexivity and the lighting the individuals receive.

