We will evaluate resident participants' baseline agitation, BPSD, affect, and sleep, based on the residents' staff caregivers' inputs and observations of the residents. We will assess agitation, BPSD, affect, and sleep using the Cohen-Mansfield Agitation Inventory (CMAI), Neuropsychiatric Inventory-Nursing Home version (NPI-NH), Philadelphia Geriatric Center Affect Rating Scale (ARS), and Pittsburgh Sleep Quality Index (PSQI), respectively,

We will measure lighting level by 1) on-site manual light, and 2) a personal light monitor, LYS button during the baseline week. The LYS button is small (1 inch), light weighted (4g), and user friendly. It has a clip at the back of the button and can be easily clipped on clothes. For a resident who does not mind having the sensor placed on clothing, we may place it on the shirt collar or shoulder. We will communicate with their caregivers so that

they are aware of the button when clothes are being changed and make sure the button is clipped back on. We will check the device on site at least twice per week and will retrieve data after each week of data collection. We will pre-set a series of algorithms determining the device use status. If the device appears not to be placed or functioning properly, the system will send a warning message to the team and we will make all attempts to check the device on site. We will manually measure light level twice a week during the baseline week. In addition, we will place a personal light monitor, LYS button, on participants, all day, 7 days a week, during the baseline week.

Aim 3: Staff and administrators

1. Screening survey: We will ask participants to fill out the survey to confirm their eligibility. If they are eligible, we will continue to the next steps.
2. Baseline survey: we will ask participants to fill out a survey to collect data about their demographics and relevant work experiences (e.g., age, race, gender, education, and professional experiences).
3. Feasibility surveys: we will ask participants to fill out the Acceptability of Intervention Measure (AIM), Feasibility of Intervention Measure (FIM), and Intervention Appropriateness Measure (AIM) to evaluate the acceptability, appropriateness, and appropriateness of the SABL intervention.
4. Qualitative interview: their evaluation on the acceptability, feasibility, and appropriateness of the SABL lighting intervention.

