7.4.6.3 Preparation and Dispensing

Describe how the test article will be assigned to each subject and dispensed. Describe the steps necessary to prepare the test article. Include where the test article preparation will be done and by whom. Fully describe how the study treatment is to be administered and by whom.

In preliminary measures, the average nursing home lighting is 250 (\pm 105) lux in bedroom, 193 (\pm 122) lux at corridor, 170-288 (\pm 106-123) lux at the dining room, and 285 (\pm 91) lux. The measures are consistent with a prior study showing that the lighting in nursing homes is largely insufficient to meet the visual needs to older adults (De Lepeleire et al., 2007).

In this study, the lighting dosage will target at 400 lux and CS=0.3 during the day and provide dim light \leq 40 lux and CS \leq 0.1 in participant bedrooms at night. The intensity and color of our SABL will be perceived like low-level daylight and does not cause any

glare. We estimate each resident will be exposed to the bright light for at least 4 hours per day (2 hours during three mealtimes and 2 hours during other daily activities). The photosensors will continuously monitor daylight situations and adjust accordingly. It is possible that participants may receive >400lux and CS>0.3 from daylight.

7.4.6.4

Return or Destruction of the Test Article

Describe the procedures for final reconciliation of the test article supply at the end of the study and whether the test article is to be shipped back to a source or destroyed on site.

[name] and his designated research assistant will collect the lighting system at the end of the study and bring it back to the lab.

7.4.6.5

Prior and Concomitant Therapy

Describe what prior and/or concomitant medical therapy will be collected. Describe which concomitant medicines/therapies are permitted during the study. Describe which concomitant medicines are not permitted during the study.

No prior or concomitant medical therapy will be provided or prohibited.

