Study Title: The Effect of Smart Ambient Bright Light for Nursing Home Residents with Alzheimer's Disease and Related Dementias (Smart Lighting Study)

PIs: [name] (Contact PI) and [name]

NCT05825404

04-24-2023

Data Analysis Plan

Aim 1: Pilot test the effect of SABL in reducing agitation in ADRD.

All data will initially be assessed with descriptive techniques to determine distributions and identify outliers. Baseline to post-intervention changes in participants' CMAI, NPI-NH, and ARS scores will be used as the outcomes in all subsequent analyses. To conduct the group analysis, each participant will serve as their own control, which allows minimal use of control variables. The effect of the intervention will be analyzed using multi-level modeling to adjust for clustering of participants at the facility level. We will use the daytime and nighttime average of lighting dosages (lux and CS) from the personal light monitors as the independent variable to analyze the effect of SABL on changes in CMAI, NPI, and ARS. Although not powered for a detailed analysis, we will explore the impact of participant characteristics (sex, age, race, ethnicity, ADRD stage, and daylight exposure) on the intervention effect by adding them as covariates to the regression model.

Aim 2: Evaluate the fidelity of the SABL delivery.

All data will initially be assessed using descriptive techniques to examine underlying assumptions and detect any violations. To assess the intervention fidelity, the lux and CS data measured via manual measurements will be analyzed using one sample t-tests to analyze lighting levels during the day and nighttime, compared to the target levels. The data from personal light monitors will be analyzed similarly at individual level. Although not powered for a detailed analysis, we will explore the impact of participant characteristics (sex, age, race, ADRD stage, co-morbidity, facility, and daylight conditions) on the lighting received based on the personal light monitor.

Aim 3: Evaluate the feasibility of implementing SABL.

The data includes ratings of acceptability, feasibility, and appropriateness. All data will be analyzed using descriptive analyses.

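### The Aim 1 model relates a change in symptoms to the level of light received with no adjustment for the resident's own week-1 light; the slope can be attenuated, by an amount the documents do not fix

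*Protocol*

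**What the plan says.** Protocol 8.3 and the SAP give the same Aim 1 model.

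- **Outcome.** Baseline-to-post differences in CMAI, NPI-NH and ARS, which "will be used as the outcomes in all subsequent analyses".
- **Exposure.** "We will use the daytime and nighttime average of lighting dosages (lux and CS) from the personal light monitors as the independent variable". The SAP ends the same sentence "as the independent variable to analyze the effect of SABL on changes in CMAI, NPI, and ARS". Protocol 2.3 confirms that received levels are meant: the team "will use the actual dosage (lux and CS levels) received by participants to analyze the intervention effect".
- **Model.** "multi-level modeling to adjust for clustering of participants at the facility level". No resident-level term is named. Section 8.3 says participants serve as their own controls, but not how this enters the model. It also does not say which monitor weeks form the average.
- **Week-1 light.** Section 7.2.1 states: "we will place a personal light monitor, LYS button, on participants, all day, 7 days a week, during the baseline week". Section 7.2 has the monitor worn again in weeks 3, 5, 7, 9, 11 and 13. A personal baseline light record is therefore collected.
- **Usual light.** Section 7.4.6.3 states: "In preliminary measures, the average nursing home lighting is 250" lux in bedrooms, with ±105. It gives 193 ±122 for corridors, 170–288 ±106–123 for dining rooms, and an unlabelled 285 ±91. It does not say what the ± measures. The daytime target in the same section is 400 lux.

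**The concern.** If symptoms respond to light, a resident's baseline score already reflects that resident's usual light. Subtracting the baseline score removes that part from the outcome. Nothing removes it from the exposure, so the two sides of the regression are on different footings.

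Take two residents who both receive 400 lux under SABL, one starting from 380 and the other from 150. They have gained 20 and 250 lux, but the model gives them the same dose. In usual-light weeks, residents whose light has not changed at all still carry different doses.

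This slope is the plan's stated estimate of the SABL effect, and Protocol 2.3 says the findings will inform later studies. A slope pulled toward zero could lead those studies to discount a real effect.

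**Working it through.** **The plan's own figure.** The plan gives none for this regression. Its one power statement (8.2: d = 0.53, alpha .05, power 0.92, 36 after attrition from 40) concerns a different calculation. A paired t-test gives 0.930 one-sided or 0.871 two-sided at n = 36, and 0.905 two-sided at n = 40. None of these involves received light, so this point neither uses nor changes them.

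**Inputs.** From 7.4.6.3: mean usual bedroom light 250 lux, target 400 lux, spread 105 lux. Assumed, because the documents do not give them:

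- the between-resident SD of usual personal light (50 or 105 lux);
- SABL-week SD of 50 lux;
- usual-light weeks equal to baseline ±30 lux;
- the correlation r between week-1 and SABL-week light;
- an effect linear in added lux;
- at first, no monitor error.

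**Case A: SABL weeks only.** If change = β(L_post − L_base) + error, the slope on L_post alone is β[1 − r × SD_base/SD_post]. With SD_post = 50:

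| r | SD_base 50 | SD_base 105 |
|---|---|---|
| 0 | 1.00 | 1.00 |
| 0.3 | 1 − 0.3 × 50/50 = 0.70 | 1 − 0.3 × 105/50 = 0.37 |
| 0.5 | 1 − 0.5 × 50/50 = 0.50 | 1 − 0.5 × 105/50 = −0.05 |

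**Case B: SABL and usual-light weeks pooled equally, no resident term, r = 0.** The slope ratio is 1 − Cov(L, L_base)/Var(L). Only the usual-light half covaries with baseline, so Cov = SD²/2. Var(L) = ½(50²) + ½(SD² + 30²) + (150/2)² = 7,325 + SD²/2.

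- SD 50: 1 − 1,250/8,575 = 0.85
- SD 105: 1 − 5,512.5/12,837.5 = 0.57

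**Within-resident comparison.** Subtracting a resident's usual-light change from the SABL change gives (L_S − L_base) − (L_C − L_base) = L_S − L_C. Week-1 light cancels. Simulation with a resident fixed effect gave 0.99 to 1.00 of the true slope.

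**Adding monitor error.** Error SD of 50 lux on each weekly average (assumed), r = 0, slope as a fraction of the truth:

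| Setting | Level alone | Change in light | Level + week-1 covariate |
|---|---|---|---|
| Pooled, SD 50 | 7,325/11,075 = 0.66 | 8,575/13,575 = 0.63 | 0.71 |
| Pooled, SD 105 | 7,325/15,337.5 = 0.48 | 12,837.5/17,837.5 = 0.72 | 0.73 |

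With SABL weeks only at SD 50, level and change both give 0.50. The covariate column is the two-predictor least-squares coefficient. At SD 50, for example, it is (7,325 × 5,000 + 1,250²)/(11,075 × 5,000 − 1,250²) = 0.71.

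**The case against.** Several points on the other side have force.

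- **The spread is not a resident SD.** Section 7.4.6.3 reports room lighting, and its ± could be across rooms, positions or times. The analysed exposure is a worn-monitor average over all the spaces a resident uses, and shared dining and activity areas should narrow it. This stands, and it is why SD 50 is shown beside 105.
- **The system is built to even out light.** Under 2.3, 7.1 and 7.4.2 the photosensors adjust the LEDs to daylight, which pushes r toward zero. At r = 0 the SABL-only slope is unbiased. But 7.4.2 also allows residents to receive more than the target from daylight, so r > 0 remains possible.
- **It is a crossover with participants as their own controls.** A resident fixed effect would remove the pooled bias. A resident random intercept is a partial repair: simulations under differing assumptions gave about 0.69 to 0.87. Since the plan names only facility-level clustering, neither can be presumed.
- **The dosing rationale is a level attained.** Under a threshold response, neither level nor linear change is correctly specified. This limits the arithmetic; it does not justify ignoring baseline light when the outcome is a change.
- **Daylight exposure is a covariate, and 7.4.25 promises model diagnostics.** The covariate is exploratory and is not week-1 light. The diagnostics are general.

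A reader might infer that the light effect will be attenuated, or will vanish. The documents do not support that, because r, the resident-level SDs and the resident term are all unstated. A reader might also infer that using change in light always restores the true slope. With monitor error it does not, and at SD 50 it does no better than the level.

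**Conclusion.** The mismatch is in the text of both documents: a change outcome, a level exposure, and no adjustment for week-1 light that is already collected. Attenuation is conditional. It requires residents' usual light to differ, together with either pooling of SABL and usual-light weeks without a resident term or a positive correlation between week-1 and SABL-week light.

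The size cannot be determined from the documents. Under the stated assumptions it ranges from no bias (SABL weeks only, r = 0) to a slope of about zero (SABL weeks only, SD 105, r = 0.5). The pooled values are 0.85 at SD 50 and 0.57 at SD 105. All of these rest on linearity in added lux and error-free monitors.

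This is a cheap improvement to the analysis text, held with moderate confidence.

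**What to change.** In Protocol 8.3 and the SAP:

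1. Keep the received light level as the exposure and add the resident's week-1 monitor average as a covariate, in the same metric (daytime or nighttime, lux or CS). In the monitor-error settings tabulated above this did better than the level alone, and without error it recovers the full slope.
2. State which weeks form the exposure average. If several follow-up weeks per resident are used, add a resident-level term.
3. Report the change-in-light model as a sensitivity analysis, because it carries monitor error from two weeks.
4. Do not substitute on-site room readings for a missing week-1 monitor record in the main model, since they measure something different. State how such residents will be handled as missing data.

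The cost is a few sentences and one extra parameter per model, plus a missing-data rule for residents without a usable week-1 record. No new data or procedures are needed.
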